## 5. CONSIDERATIONS FOR DATA ANALYSES AND DATA HANDLING CONVENTIONS

### 5.1. Study Treatment & Sub-group Display Descriptors

Treatment Group Descriptions			
RandAll NG		Data Displays for Reporting	
Code	Description	Description	Order in TLF
	This will be derived as subjects who did not receive any treatment	No Treatment	1
	This will be derived as subjects in RandALL codes A or C	All Placebo	2
	This will be derived as subjects in RandALL codes B or D	All NEMI	3
A	Placebo	Placebo Diskus	4
B	GSK2269557 1000 mcg	NEMI Diskus	5
C	Placebo via Ellipta	Placebo Ellipta	6
D	GSK2269557 700 mcg	NEMI Ellipta	7

#### NOTES:

- The following footnote will be presented on displays which use the "Placebo Diskus", "NEMI Diskus", "Placebo Ellipta" or "NEMI Ellipta" treatment groups:  
NEMI Diskus =1000 mcg Nemiralisib administered via the Diskus device; NEMI Ellipta =700 mcg Nemiralisib administered via the Ellipta device
- Order represents treatments being presented in TFL, as appropriate

Treatment groups "Placebo" and "Placebo via Ellipta" (RandAll NG codes A and C) will be combined into "All Placebo" treatment group. Similarly, treatment groups "GSK2269557 700 mcg" and "GSK2269557 1000 mcg" (RandAll NG codes B and D) will be combined into "All NEMI" treatment group.

Treatment comparisons will be displayed as follows using the descriptors as specified:

- All NEMI vs All Placebo

#### Notes:

- The "All Placebo" and "All NEMI" groups and "All NEMI vs All Placebo" treatment comparison will be presented for Pharmacodynamic and biomarker, efficacy and study population summaries unless otherwise specified.
- The "Placebo Diskus", "NEMI Diskus", "Placebo Ellipta" or "NEMI Ellipta" treatment groups will be presented for Pharmacokinetic and safety summaries unless otherwise specified.
- The "Placebo Diskus", "NEMI Diskus", "Placebo Ellipta" or "NEMI Ellipta" treatment groups will be presented for all listings

## 5.2. Baseline Definitions

For all endpoints (except as noted in baseline definitions) the baseline value will be the latest pre-dose assessment with a non-missing value, including those from unscheduled visits. If time is not collected, Day 1 assessments are assumed to be taken prior to first dose and used as baseline.

Parameter	Study Assessments Considered as Baseline				Baseline Used in Data Display
	Screening	Day 1 (Pre-Treatment)	Day 2 Within 48H/discharge (On Treatment)	Day 12 (On Treatment)	
Safety					
Labs including Haematology	X	X			Day 1
ECG	X	X			Day 1
Vitals	X	X			Day 1
Efficacy					
HRCT Untrimmed	X				Screening
HRCT Scan Trimmed					
Screening&Day12	X				Screening
Screening&Day28	X				Screening
Day12&Day28				X	Day 12
FEV 1 and FVC		X	X		Day 1 
Daily PEF 		X			Day 1
					Mean of Days 1 to 3
					Maximum of Days 1 to 3
Pharmacodynamic					
Sputum and Blood	X				Screening
Genetic sample (PGx) 			X		

### NOTES:

- Unless otherwise stated, the mean of replicate assessments at any given time point will be used as the value for that time point.
- [1] Baseline will be investigated to ensure there is sufficient data and will be footnoted as appropriate
- [2] For PEF 3 different baselines will be calculated: Day 1, mean of Days 1 to 3 and Maximum of Days 1 to 3. TFLs will be footnoted with the relevant baseline.
- [3] Collected at any time after randomisation

Unless otherwise stated, if baseline data is missing no derivation will be performed and baseline will be set to missing.

### 5.3. Examination of Covariates and Subgroups

#### 5.3.1. Covariates and Other Strata

The list of covariates may be used in descriptive summaries and statistical analyses, some of which may also be used for subgroup analyses. Additional covariates of clinical interest may also be considered.

Category	Details
Covariates	Age, Sex, BMI, Country, Primary exacerbation severity

#### 5.3.2. Examination of Subgroups

The list of subgroups may be used in descriptive summaries and statistical analyses. Additional subgroups of clinical interest may also be considered.

- If the percentage of subjects is small within a particular subgroup, then the subgroup categories may be refined prior to unblinding the trial.
- If the category cannot be refined further, then descriptive rather than statistical comparisons may be performed for the particular subgroup.

Subgroup	Categories
Primary exacerbation severity	Moderate or Severe 
Country	Country

#### NOTES:

[1] Exacerbations are defined as severe if they require hospitalisation, otherwise they are defined as moderate

### 5.4. Other Considerations for Data Analyses and Data Handling Conventions

Other considerations for data analyses and data handling conventions are outlined in the appendices:

Section	Component
13.3	Appendix 3: Assessment Windows
13.4	Appendix 4: Study Phases and Treatment Emergent Adverse Events
13.5	Appendix 5: Data Display Standards & Handling Conventions
13.6	Appendix 6: Derived and Transformed Data
13.7	Appendix 7: Reporting Standards for Missing Data
13.8	Appendix 8: Values of Potential Clinical Importance

## 6. STUDY POPULATION ANALYSES

### 6.1. Overview of Planned Study Population Analyses

The study population analyses will be based on the “All Subjects” population, unless otherwise specified.

Study population analyses including analyses of subject’s disposition, protocol deviations, demographic and baseline characteristics, prior and concomitant medications, and exposure and treatment compliance will be based on GSK Core Data Standards. Details of the planned displays are presented in [Appendix 10: List of Data Displays](#).

## 7. PHARMACODYNAMIC AND BIOMARKER ANALYSES

### 7.1. Primary Pharmacodynamic and Biomarker Analyses

#### 7.1.1. Endpoint / Variables

Sputum RNA will be extracted and hybridised using a balanced batch design. An appropriate microarray platform will be determined at the time of hybridisation, to allow for improvements in technology. The quality of the data will be assessed and then normalised using appropriate methodologies and software.

Microarray mRNA data will be normalised using gcRMA or RMA in Array Studio v5.0 or later. After normalisation, the data will be quality assessed and any samples deemed as QC fails will be excluded from any further analysis. This quality assessment will involve looking for outlying signals in both the normalised expression data and the MAS5 QC metrics generated from each sample. If any samples are excluded, the remaining data will be re-normalised. The output from the normalisation will be log2 transformed mRNA intensity data (measured in arbitrary units).

Since the data will be log2 transformed prior to the analysis the treatment effects will be expressed as ratios after back transformation ( $2^x$ ). These ratios can be converted to fold change values as follows:

- If ratio  $\geq 1$  then fold change = ratio
- If ratio  $< 1$  then fold change =  $-1/\text{ratio}$

Microarray data consists of expression values (log2-transformed) derived from individual probe sets designed against coding regions of individual genes. More than one probe set can exist per gene. This analysis will be conducted at the probe set level.

The mRNA data gives results from ~14000 genes encoded by ~54000 probe sets. To establish the PI3K $\delta$ -dependent changes in previously identified immune cell mechanisms specifically related to neutrophil function using mRNA, we identified 258 gene to subset our data on, refer to Section [13.6.5](#). The gene names were converted to Affymetrix probe IDs, this resulted in 638 probes refer to Section [13.6.5](#).

To compare the expression value between treatments for each probe set, linear repeated measures mixed effects model will be fitted to each probe set, with log2 (intensity) as the response variable. Note: log2 (intensity) may also be referred to as mRNA intensities (logarithm base 2 scale). Alteration in previously identified immune cell mechanisms specifically related to neutrophil function will be determined by changes in mRNA transcriptomics in induced sputum after 12, 28 and 84 days of treatment by the analysis of mRNA intensities (logarithm base 2 scale) subset by the 638 probes identified in Section 13.6.5.

**7.1.2. Summary Measure**

A repeated measures modelling analysis will be performed on the subset of 638 probes which have previously identified immune cell mechanisms specifically related to neutrophil function.

The model will be used to estimate the baseline adjusted fold changes for active treatment and placebo calculated for Day 12, Day 28 and Day 84 along with the corresponding 95% confidence intervals and unadjusted P-values. Additionally, baseline adjusted ratios of the change between active treatment and placebo will be calculated along with 95% confidence intervals and unadjusted P-values.

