## 2.4. Statistical Analyses

### 2.4.1. Primary Analyses

To estimate differences in mRNA intensities within and between treatment groups, a repeated measures model will be fitted to the results of the analysis of each probe set at Day 12, Day 28 and Day 84 following a loge transformation of the data. The Day 1 response will be fitted as a baseline covariate.

Back transformed ratios versus screening along with 95% confidence intervals will be calculated for each treatment group and timepoint. Additionally, baseline adjusted ratios of the change between active treatment and placebo will be calculated along with 95% confidence intervals.

Further details are provided in Section 7.1.

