**7.1.4.1. Statistical Methodology Specification**

Endpoint / Variables

 
Alterations in the previously identified immune cell mechanisms specifically related to neutrophil function as determined by changes in mRNA transcriptomics in induced sputum after 12, 28 and 84 days of treatment. The response variable will be mRNA intensities (logarithm base 2 scale).
 

Model Specification
The mRNA data gives results from ~14000 genes encoded by ~54000 probe sets. A subset of 638 probe sets specifically relating to the cell mechanisms of neutrophil function is specified in Section 13.6.5 This subset will comprise the primary statistical analysis dataset.

Each probe set will be analysed separately.

The log2 transformed mRNA intensities will be analysed in a repeated measures model under a Frequentist framework. The model will include a Treatment, Visit and Treatment\*Visit term. The Visit will consist of 4 levels: Screening (Baseline), Day 12, Day 28 and Day 84, and the Treatment will consist of three levels: Null (when Visit = Screening), All Placebo and All NEMI. An unstructured (UN) covariance structure will be fitted. The denominator degrees of freedom for use in significance testing will be computed using the Kenward Rogers approximation.

Back transformed baseline-adjusted ratios along with 95% CIs and two-sided unadjusted p-values will be calculated for each Visit for the All NEMI and All Placebo Treatments, i.e. Day 84, Day 28 and Day 12 in the All NEMI Treatment group vs Screening and Day 84, Day 28 and Day 12 in the All Placebo Treatment group vs Screening. Additionally, baseline adjusted ratios between All NEMI vs All Placebo will be calculated for Day 12, Day 28 and Day 84 along with 95% CI and two-sided unadjusted p-values, i.e. Day 84 in the All NEMI Treatment group vs Day 84 in the All Placebo Treatment group, similarly for Day 28 and Day 12. Other comparisons of interest may also be calculated such as means for each Visit and Treatment, i.e. Screening (Null Treatment), Day 12, 28 and 84 (All NEMI Treatment) Day 12, 28 and 84 (All Placebo Treatment).

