To enable review by the study team, csv files will be created containing the output for all probe sets in scope for the primary statistical analysis will be generated sorted alphabetically by probe set ID. Separate csv files may be created containing only probe sets where the p-value for the comparisons is <0.05. Such probe sets will be ranked by fold change, with the expectation that, in general, a greater than a 1.5-fold change is scientifically meaningful. To comply with guidance regarding QC, csv files will be stored as a SAS dataset to ensure QC can be audited.

Following review by the study team of the results, a subset of probe sets may be identified and may be used for further reporting.

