##### RNA transcriptome

- Affymetrix microarray mRNA data will be normalised using RMA in ARRAY STUDIO v8.0 or later by the Statistical Consultancy Group (SCG) within GSK. After normalisation, the data will be quality assessed and any samples deemed as QC fails will be excluded from any further analysis. This quality assessment will involve looking for outlying signals in both the normalised expression data and the MAS5 QC metrics generated from each sample. If any samples are excluded, the remaining data will be re-normalised. The output from the normalization will be log2 transformed mRNA intensity data.
- Summary mRNA data will be reviewed and a decision made on which probe sets are to be included in the SI dataset.
- Treatment ratios from the statistical analyses of mRNA intensity data will be converted to fold changes as follows:
  - If ratio  $\geq 1$  then fold change = ratio
  - If ratio  $< 1$  then fold change =  $-1/\text{ratio}$

The primary pharmacodynamic endpoint is based on a subset of probe sets defined as those that have previously identified immune cell mechanisms specifically related to neutrophil function.

The gene list that meets this criterion based on PII115119 D14 vs D1 gene changes, PII115117 and Metacore neutrophil pathways identified in PII115119 study. This gene list identified 258 genes in total after filtering for redundancy and was agreed by the study team is presented in [Table 3](#).

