13.10.9. Pharmacodynamic and Biomarker Tables

Pharmacodynamic and Biomarker: Tables					
No.	Population	IDSL / TST ID / Example Shell	Title	Programming Notes	Deliverable
MRNa					
6.1.	All Subjects	PII115119/ Part A/ Listing 40	Summary of Statistical Analysis of mRNA Transcriptome in Induced Sputum (Selected Probe Sets Related to Neutrophil Function)	Summarise ratio, 95% CI and p-values. Sort alphabetically on probe set ID	SAC
6.2.	All Subjects	PII115119/ Part A/ Listing 40	Summary of Statistical Analysis of mRNA Transcriptome in Blood (All Probe Sets)	Biostatistics will await guidance following unblinded regarding which, if any, probe sets should be presented for the exploratory analysis and confirmation if a cut off criteria other than p-value<0.05 AND (fold change> 1.5 OR fold change< -1.5) should be used in determining which comparisons for the probe sets should be presented. Summarise ratio, 95% CI and p-values.	SAC

Pharmacodynamic and Biomarker: Tables					
No.	Population	IDSL / TST ID / Example Shell	Title	Programming Notes	Deliverable
6.3.	All Subjects	PII115119/ Part A/ Listing 40	Summary of Additional Statistical Analysis of mRNA Transcriptome in Induced Sputum (All Probe Sets)	Biostatistics will await guidance following unblinded regarding which, if any, probe sets should be presented for the exploratory analysis and confirmation if a cut off criteria other than p-value<0.05 AND (fold change> 1.5 OR fold change< -1.5) should be used in determining which comparisons for the probe sets should be presented. Summarise ratio, 95% CI and p-values.	SAC
Cell Count Data and PMN Differentials					
6.4.	All Subjects	PII115119/ Part A/Table 5.7	Summary Statistics (Absolute): Total Cell Count Data in Sputum by Treatment and Time.	Appropriate transformation should be used prior to summarising data. Ensure transformation is clearly documented and update column labels as appropriate	SAC
6.5.	All Subjects	PII115119/ Part A/Table 5.8	Summary Statistics (Change from Baseline): Total Cell Count Data in Sputum by Treatment and Time	Appropriate transformation should be used prior to summarising data. Ensure transformation is clearly documented and update column labels as appropriate	SAC

Pharmacodynamic and Biomarker: Tables					
No.	Population	IDSL / TST ID / Example Shell	Title	Programming Notes	Deliverable

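### The primary mRNA analysis reports 1,914 unadjusted NEMI vs placebo p-values with no false discovery measure beside them; a q-value column would be a cheap improvement

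*SAP*

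**What the plan says.** Section 2.4.1 frames the primary analysis as estimation: "To estimate differences in mRNA intensities within and between treatment groups, a repeated measures model will be fitted". Section 7.1.4.1 fixes the scope: "A subset of 638 probe sets specifically relating to the cell mechanisms of neutrophil function is specified in Section 13.6.5". Each probe set has its own model, and "baseline adjusted ratios between All NEMI vs All Placebo will be calculated for Day 12, Day 28 and Day 84". Section 7.1.2 says of the same contrasts that "baseline adjusted ratios of the change between active treatment and placebo will be calculated along with 95% confidence intervals and unadjusted P-values"; Section 7.1.4.1 also labels the p-values unadjusted and makes them two-sided. Section 7.1.1 says that alteration in the neutrophil mechanisms is to be judged from these results.

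The family was fixed in advance. Of the gene list, Section 13.6.5 says: "This gene list identified 258 genes in total after filtering for redundancy and was agreed by the study team". The primary results table is complete; the programming note for Table 6.1 reads "Summarise ratio, 95% CI and p-values. Sort alphabetically on probe set ID". Csv files with all in-scope probe sets are also sorted by probe set ID.

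Selection enters in two optional places in Section 7.1.4.1. First, "Separate csv files may be created containing only probe sets where the p-value for the comparisons is <0.05"; these probe sets are ranked by fold change, with a change above 1.5-fold generally expected to be scientifically meaningful. Second, "Following review by the study team of the results, a subset of probe sets may be identified and may be used for further reporting". By contrast, the exploratory analysis in Section 7.2.4 uses p<0.05 together with a 1.5-fold change as its default display cut-off.

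Nowhere does the SAP mention a q-value, a false discovery rate, a global or gene-set test, or an expected number of chance findings for the primary analysis.

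**The concern.** A p<0.05 list drawn from several hundred probe sets mixes true and chance findings in a proportion that the plan never estimates. Ranking by fold change does not separate them, because at about 15 subjects per arm a chance result on a noisy probe set can also show a large fold change. If a subset is then chosen for further reporting, its readers see p-values that look persuasive one by one but were picked from 638 per visit.

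A reader could multiply 638 by 0.05, but that is a poor yardstick for one observed list. Several probe sets map to the same gene and many genes are co-regulated, so the chance count can lie far from its mean. A q-value is computed from the observed p-values and is read beside each result.

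The wording of the filter adds a smaller problem: it refers to the comparisons in general. If within-arm changes from screening qualify, probe sets may be listed for a change that has nothing to do with the drug.

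**Working it through.** The SAP states no error rate, power or expected false positive count, so there is no plan figure to reproduce.

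**Inputs from the SAP**
- 638 probe sets, one model each; Days 12, 28 and 84; two-sided unadjusted p-values; optional cut-off p<0.05 (Section 7.1.4.1).
- A change above 1.5-fold as the yardstick of relevance (Section 7.1.4.1): log2(1.5) = 0.585.
- About 15 subjects per arm with sputum at all time points (Section 2.3).

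**Assumptions, not in the SAP**
- Between-subject SD on the log2 scale of 0.5 or 0.75; 5%, 10% or 20% of probe sets (32, 64 or 128) truly changed 1.5-fold at all visits; correlation between probe sets of 0 to 0.3.
- A two-sample t-test at each visit, 28 df, as a stand-in for the planned repeated measures model.

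**1. Number of tests**
- Between arms: 638 x 3 = 1,914.
- Within arm: 638 x 3 x 2 = 3,828. Total 5,742.

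**2. Chance findings at p<0.05 with no drug effect**
- Per visit: 638 x 0.05 = 31.9. Over three visits: 1,914 x 0.05 = 95.7 tests. These means do not need independence.
- The spread does depend on correlation. Simulated per-visit medians are 32, 26 and 22, and central 95% ranges 22 to 43, 12 to 89 and 7 to 119, at correlations 0, 0.2 and 0.3.

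**3. The same if an observed change above 1.5-fold were also required**
- SD 0.5: standard error = 0.5 x sqrt(2/15) = 0.183; 0.585/0.183 = 3.20; two-sided tail 0.00136; 638 x 0.00136 = about 0.9 per visit.
- SD 0.75: standard error = 0.75 x sqrt(2/15) = 0.274; 0.585/0.274 = 2.14; two-sided tail 0.0327. Requiring p<0.05 as well gives a joint probability of 0.0288; 638 x 0.0288 = about 18 per visit.

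**4. False share of a p<0.05 list when some probe sets truly change**

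False share = (638 - k) x 0.05 / [(638 - k) x 0.05 + k x power], where k is the number truly changed. Power for a true 1.5-fold change is 0.87 at SD 0.5 and 0.54 at SD 0.75.
- SD 0.5, k = 32: 30.3 / (30.3 + 27.9) = 52%. k = 128: 25.5 / (25.5 + 111.5) = 19%.
- SD 0.75, k = 32: 30.3 / (30.3 + 17.3) = 64%. k = 128: 25.5 / (25.5 + 69.2) = 27%.

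Simulation, including correlated probe sets, gives 18-52% and 27-64%.

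**5. For comparison, a hard cut at q<0.10 over the 1,914 tests**
- False share about 8-9%.
- Power for a true 1.5-fold change falls from 0.87 to 0.46-0.74 (SD 0.5) and from 0.54 to 0.05-0.19 (SD 0.75).

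**The case against.** The strongest reply is that this is a disclosed choice in a small mechanistic study. The aim is estimation, the p-values are called unadjusted, and no alpha, hypothesis or success rule is attached to the 638 probe sets, so no claimed error rate is broken. The gene list came from earlier studies and named pathways. All of this stands, and it is why the point is an improvement to the plan and not the correction of an error. It does not supply the missing quantity: calling a p-value unadjusted does not tell the reader what share of a shortlist is chance, and the 31.9 is already counted within the pre-specified list.

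Three stronger readings are tempting, and the document does not support them.

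- *The primary results are filtered at p<0.05.* They are not. Table 6.1 and the main csv files carry every in-scope probe set. The superseded RAP bound in the same file did report only the p<0.05 subset, but the current text does not.
- *The later subset has no guide at all.* It has one: the 1.5-fold expectation. If applied together with p<0.05 it would work well at SD 0.5 (false share 1-5%, power about 0.50) and poorly at SD 0.75 (19-53%, power about 0.47). In the primary analysis it is only an expectation attached to a ranking.
- *The p<0.05 screen must give way to a fixed q cut-off.* At SD 0.75 that could nearly empty the shortlist, as step 5 of the working shows. It is a trade-off for the sponsor.

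The t-test stand-in may also understate power: about 45 subjects are to be randomised, and a repeated measures model can use incomplete subjects. At 22 per arm and SD 0.75, power at p<0.05 would be 0.71 instead of 0.54. The 31.9 is unaffected.

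**Conclusion.** The omission is real but limited in reach. The SAP produces 1,914 between-arm p-values for its primary endpoint with no false discovery measure beside them. The exposure lies in the optional p<0.05 files and the optional subset, not in Table 6.1 as a whole.

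The count of tests and the mean of 31.9 per visit follow from the SAP alone. The effect of the 1.5-fold yardstick, the false shares and the power figures rest on the assumed SDs, true shares and stand-in test, and should be read as ranges. They show that the yardstick alone cannot be relied on: whether it nearly clears the chance findings or leaves more than half of them depends on an SD that the SAP does not give.

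**What to change.** In Section 7.1.4.1:

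- Add Benjamini-Hochberg q-values computed across the 1,914 NEMI vs placebo tests (638 probe sets x 3 visits).
- Show q beside ratio, 95% CI and unadjusted p in Table 6.1, in all csv files including any p<0.05 file, and for any subset taken forward.
- State that ratios with 95% CIs for all 638 probe sets are the main output, and that unadjusted p-values and within-arm changes are descriptive.

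The p<0.05 screen may remain as a shortlist as long as q is shown. Replacing it with a fixed cut-off such as q<0.10 is the sponsor's choice and not part of this fix.

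The cost is one extra column and two sentences, with no new data and no new models. The downside is presentational: at about 15 per arm, many probe sets with p<0.05 will show unimpressive q-values, some of them true 1.5-fold changes. None of them leaves Table 6.1.
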